Incisional negative pressure wound therapy for preoperatively irradiated pelvis and lower extremity soft tissue sarcoma wounds. A prospective, randomized pilot trial.

NCT02638298

Date Last Modified: April 21st, 2023

Principal investigator

[name]., MSCR

Associate [name]
Orthopaedic Oncology
Director of Orthopaedic Research
Associate Program Director
Medical University of South Carolina

[name]
[name]
[contact]
[contact]

Table of Contents

Hypothesis/Specific Aims.....	3
Background and Significance.....	3-5
Research Design.....	5-8
Methods.....	8-10
Budget.....	11-12
References.....	13

**Medical University of South Carolina
Protocol
PI Name: [name], MSCR**

Study Title: Incisional negative pressure wound therapy for preoperatively irradiated pelvis and lower extremity soft tissue sarcoma wounds. A prospective, randomized pilot trial.

A. HYPOTHESIS/SPECIFIC AIMS

The hypothesis of the proposed study is that use of a negative pressure wound therapy (NPWT) dressing on preoperatively radiated pelvic and lower extremity soft tissue sarcoma surgical wounds will significantly reduce the incidence and cost of wound complications.

This hypothesis will be tested through accomplishing the following specific aims:

- 1) Specific Aim 1- To estimate the wound complication rate of post-operative negative pressure dressings and traditional dry dressings, and risk of secondary interventions after resection of soft tissue sarcoma in lower extremities and the pelvis that have received pre-operative radiation. Wound complications are defined as a superficial infection, deep infection, need for prolonged (> 3 weeks) wound packing, or return to the operating room within six months for a secondary procedure. A secondary analysis of frequency and likelihood of antibiotic usage, pain scores, and functional scores will be analyzed in each group.
- 2) Specific Aim 2- To estimate the total cost of care and resource utilization in patients treated with negative pressure wound therapy and traditional dry dressings.

B. BACKGROUND AND SIGNIFICANCE

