Enrollment of subjects from each institution will be centrally regulated through the primary center, The Medical University of South Carolina. Subjects will be accrued primarily through clinic referrals to a regional musculoskeletal oncologist for evaluation of soft tissue mass. Additionally subjects may be self-referred or present to a regional referral center's hospital or emergency department. The standard of care for these patients is after a tissue diagnosis is rendered showing the mass to be a soft tissue sarcoma and appropriate staging studies are complete that the patients will receive preoperative external beam radiation. After radiation (2-6 weeks) surgery is performed for local control. The investigative portion of the study will begin in the operating room after the surgical procedure is complete. Patients evaluated who meet the inclusion/exclusion criterion (see below) will be asked by study investigators whether or not they would like to participate in this study. Informed consent for participation in the study will take place in the clinic setting (often at the time of consent for surgery) after a biopsy has shown a sarcoma and the treatment plan is to include preoperative radiation and surgical excision (which would be the standard of care). Participation will be voluntary. Patients will be randomized before or at the time of surgery to receive standard dry gauze dressing or Prevena™ dressing.

Prior to or at the time of surgery the patients will be randomized to receive either a NPWT dressing or standard dry gauze dressing. This study is not amenable to blinding given the nature of dressing and the application by the surgeon. Randomization will be done by block randomization per site.

Compensation will not be provided to patients. Our goal is to obtain a total of 160 subjects with at least 6 month follow-up, approximately 75 subjects per treatment arm. (see sample size calculations)

Inclusion Criterion:

- Age>18
- Willing to consent to randomization and able to participate in the study
- Lower extremity or pelvic soft tissue sarcoma necessitating radiation prior to surgical resection
- Primary closure of wound
- Patients scheduled for surgical resection

Exclusion Criterion:

- Flap coverage or skin graft
- Patients scheduled for amputations as local control of their tumor
- Sarcomas where radiation is not planned preoperatively
- Repeat surgeries for oncologic reasons (positive margins)
- Known allergy to adhesive tape

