- Recurrent soft tissue sarcoma

Consent:

Subjects will be consented for participation in the study by one of the aforementioned investigating surgeons (or research team) at the time of their evaluation in the clinic or hospital setting. Consent will include permission to randomize dressing to either to negative pressure wound therapy or “standard” dry gauze post-surgical dressing. Standardized study consent forms will be signed by the investigating surgeon and the patient. Standard surgical consent for the assigned procedure will be done in accordance with the standard of care.

Randomization:

Randomization will be predefined at each site using block randomization to ensure that each site is balanced for each arm of the study. This block randomization will be distributed and managed centrally at The Medical University of South Carolina. The randomization process will be performed centrally at MUSC and the treating surgeon will not have access to that randomization list. Preoperatively, the subjects will be blinded as to which dressing will be used for surgical wound coverage, but which dressing (i.e. which treatment arm) the patient was randomized to receive will be apparent postoperatively. Due to the design of the study, the surgeons are not able to be blinded.

Preoperative Evaluation:

Patients will receive the standard workup of a soft tissue sarcoma. The patient’s preoperative evaluation or treatment plan will not be affected by this investigation or the subjects desire to participate. Data collected preoperatively will include radiation type and dose, use of chemotherapy, VAS pain score, MSTS score, PROMIS Global Health score, medical comorbidities, tumor location, and any use of pain medicines.

Operative Intervention:

Surgery will be done in accordance with the standard of care for the excision of soft tissue sarcomas.

Anesthesia: Either regional or general anesthesia will be performed at the discretion of the treating physicians. Skin will be closed with either staples or 2-0 nylon sutures and a temporary closed suction drain may be placed. The use and duration of the drain will be at the surgeon’s discretion and in accordance with practice.

Tumor excision/limb reconstruction:

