No validated system is designed to specifically assess surgical wounds. The CDC definition is a stringent criterion to classify surgical site infection (SSI). Infections will be classified as superficial or deep and acute or delayed. Acute infection will be defined as within 6 weeks of the surgical procedure. Delayed or late infection will be defined as greater than 6 weeks from the surgical procedure.

Criteria for wound complication (SSI or surgical site infections)-

Table 1

SUPERFICIAL INFECTION (SSSI)	DEEP INFECTION (DSSI)
Involves skin and subcutaneous tissue (and)	Involves deep soft tissues (and)
a) purulent drainage	a) purulent drainage
b) organism cultured aseptically from wound	b) deep wound that spontaneously dehisces or is deliberately opened
c) deliberate opening of wound	c) an abscess or other evidence of deep infection
d) diagnosis of SSI by attending surgeon	d) diagnosis of SSI by attending surgeon

Superficial infection-

Infection occurs after any operative procedure,

and

involves only skin and subcutaneous tissue of the incision

and

patient has at least one of the following:

- a. purulent drainage from the superficial incision.
- b. organisms isolated from an aseptically-obtained culture of fluid or tissue from the superficial incision.
- c. superficial incision that is deliberately opened by a surgeon and is culture-positive or not cultured *and*
patient has at least one of the following signs or symptoms: pain or tenderness; localized swelling; redness; or heat. A culture negative finding does not meet this criterion.

d. diagnosis of a superficial incisional SSI by the surgeon or attending physician.

Deep infection-

Infection occurs after the operative procedure *and* involves deep soft tissues of the incision (e.g., fascial and muscle layers) *and* patient has at least one of the following:

- a. purulent drainage from the deep incision.
- b. a deep incision that spontaneously dehisces or is deliberately opened by a surgeon and is culture-positive or not cultured *and* patient has at least one of the following signs or symptoms: fever ($>38^{\circ}\text{C}$); localized pain or tenderness. A culture-negative finding does not meet this criterion.
- c. an abscess or other evidence of infection involving the deep incision that is found on direct examination, during invasive procedure, or by histopathologic examination or imaging test.
- d. diagnosis of a deep incisional SSI by a surgeon or attending physician.

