Data will be stored on the MUSC RedCAP database system. Protocol information such as unanticipated problems, adverse events, findings that change risks to patients, confidentiality loss, changes to protocol, and interim analysis findings will be discussed at monthly conference call meetings of all coordinating investigators.

Data Management:

All paper data will be stored at the clinical sites in locked file cabinets in compliance with institutional and federal policies for the storage of personal health information. Electronic data will be stored on the institutional protected hard drive. Study specific data such as survey results will not be made part of the

patient's permanent electronic medical records. Only study investigators will be given access to these files. Data will be stored on the institutional REDCap database. Patients from all sites will be given unique identifiers prior to input into REDCap.

Data safety and monitoring will be completed by the Principle Investigator. The PI will review and report any adverse events, protocol deviations/violations, early stopping rules and internal audit results. In addition to the oversight of data safety the PI will be responsible for identifying, reviewing monthly, and reporting adverse events. Data from other institutions will be reviewed by the study team and PI on a semi-annual basis.

Statistical Considerations: Statistics will be managed through MUSC Biostatistics core.

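### The plan puts interim analysis findings on the calls of all coordinating investigators without limiting them to pooled data, so by-arm results may reach the unblinded surgeons who determine the endpoint

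*Combined protocol and SAP*

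**What the plan says.** Section E (Methods), Coordination of all sites, lists topics for the investigators' calls. Alongside unanticipated problems, adverse events and protocol changes, it states that "interim analysis findings will be discussed at monthly conference call meetings of all coordinating investigators". The content of those findings is not described.

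Four other parts of the protocol bear on this:

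- **Blinding.** Section D (Research Design) says "This study is not amenable to blinding given the nature of dressing and the application by the surgeon", and its Randomization paragraph repeats that "the surgeons are not able to be blinded". The same paragraph keeps the allocation list central and out of the treating surgeon's hands.
- **Endpoint.** Specific Aim 1 sets the composite, with a six-month window for reoperation: "Wound complications are defined as a superficial infection, deep infection, need for prolonged (> 3 weeks) wound packing, or return to the operating room". Under the infection definitions in Section D, any one of criteria a to d is enough once the tissue level is met. Criterion d is "diagnosis of a superficial incisional SSI by the surgeon or attending physician" and, for deep infection, "diagnosis of a deep incisional SSI by a surgeon or attending physician".
- **Monitoring.** Data Management gives data and safety monitoring to the PI. It mentions early stopping rules without stating any, and has other sites' data reviewed twice a year.
- **Analysis.** Analytic Approaches makes the primary analysis the complication rate in each arm with an exact binomial 95% interval. Fisher's test between arms is secondary and is described as underpowered. No interim analysis is defined.

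**The concern.** In an open-label trial, a surgeon who knows one patient's dressing does not yet know which dressing is ahead across all sites. Knowing the running result by arm gives a judgement-based threshold a direction. The endpoint here has room for that. Clinical diagnosis alone can count as an event, and prolonged packing and return to theatre are also decisions of the treating team. The documents describe no blinded adjudication, closed session or independent committee that would stand between interim results and these decisions.

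What is at stake is the primary output. If thresholds drift in opposite directions after results are shared, both arm rates and their difference are biased. The exact interval describes sampling error only, so the reported precision would give no sign of it. Planning of any later definitive trial from these rates would inherit the error.

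**Working it through.** **1. Does the text permit by-arm results to reach those who determine the endpoint?**

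| Link | Source | Status |
|---|---|---|
| Interim findings go to all coordinating investigators | E, Coordination of all sites | Stated |
| Findings limited to pooled data | – | Not stated anywhere |
| Coordinating investigators include operating surgeons | B (final part, on the collaborating oncology group and its sites); D, Consent (investigating surgeons obtain consent) | Inferred |
| Surgeons know the arm | D, Research Design and Randomization | Stated |
| Surgeon or attending diagnosis is sufficient for infection | D, infection definitions, criterion d | Stated |
| Findings are displayed by arm | – | Not stated; permitted by silence |

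The route is open as the text stands. That it will be used is not stated.

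**2. Reproducing the plan's precision figures**

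Inputs, from the sample size justification: 4 sites × 40 patients = 160; less 5 per group, (160 − 10)/2 = 75 evaluable per arm.

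Clopper-Pearson interval for x events in n: lower limit = Beta(0.025; x, n − x + 1), upper limit = Beta(0.975; x + 1, n − x).

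At x = 15, n = 75 (20%): 11.6% to 30.8%, half-width 9.6 points. This agrees with Table 3. The protocol's figures are not in dispute.

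**3. What a given drift would do**

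The documents give no drift figure, so k below is an assumption. Start with equal arms at 15 of 75. Suppose k diagnoses are gained in one arm and k lost in the other. Each arm's rate moves by k/75, and the spurious difference is 2k/75.

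| k (assumed) | Events | Rates | Shift per arm | Spurious difference |
|---|---|---|---|---|
| 1 | 16 v 14 | 21.3% v 18.7% | 1.3 points | 2.7 points |
| 3 | 18 v 12 | 24.0% v 16.0% | 4.0 points | 8.0 points |
| 5 | 20 v 10 | 26.7% v 13.3% | 6.7 points | 13.3 points |

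At k = 3 the reported exact intervals would be 14.9% to 35.3% and 8.6% to 26.3%, with half-widths of 10.2 and 8.9 points. These are the widths for true counts of 18 and 12; nothing in them allows for drift. Fisher's two-sided p is 0.31, so the shift would not look like a significant finding. It would simply be carried in the estimates.

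**The case against.** **Frequency.** A reader might infer that interim results go out every month. The documents do not support that. Monthly is how often the calls take place; no frequency is given for interim analyses, and the only review interval for other sites' data is semi-annual. This stands.

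**Display by arm.** A reader might also infer that comparative results are definitely released. The sentence does not say so, and in a list of general coordination topics it may be no more than standard wording. This stands as a limit on the claim, but it does not remove the point. It is the only rule on who sees interim findings, and no other provision narrows it.

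**False positives.** Repeated looks do raise the chance that a nominal p ≤ 0.05 appears at some time. With two equal arms at 20% or 30%, outcomes known at once and equally spaced unadjusted Fisher tests (all assumptions), that chance is about 3% for one look, 8–9% for six and 12–13% for 36. But no p-value triggers any action in this plan, and the between-arm test is secondary in an estimation pilot. These figures do not measure bias in the arm rates and should not be used as the size of the problem.

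**Enrolment.** A reader might infer that shared trends would equally distort who is enrolled. The central, withheld list makes that risk smaller. Anticipating the next allocation would mean guessing within site blocks, whose size is not given.

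**Bias already present.** Unblinded surgeons testing a hypothesis that favours NPWT diagnose the endpoint whether or not results are shared. That is true, and limiting the calls leaves it in place. The calls add an increment of unknown size, but unlike the open-label design that increment is avoidable.

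**Conclusion.** The concern holds as a gap in safeguards, not as a demonstrated bias. The protocol provides for interim findings to be discussed with all coordinating investigators and sets no limit to pooled data, while surgeon judgement made with knowledge of the arm can by itself create an endpoint event. This could bias the arm-specific complication rates during accrual and follow-up.

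Its size cannot be determined from the documents. The 18 v 12 example is illustrative: it rests on an assumed 3 diagnoses moved in each arm, and its 4-point shift per arm lies inside the 9.6-point half-width at 20%. The conclusion also rests on the inference that coordinating investigators include the diagnosing surgeons. It is a cheap improvement.

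**What to change.** Revise the sentence under Coordination of all sites so that the calls receive pooled accrual, adverse-event, risk and protocol information, not split by arm. Add that outcome results by arm stay with the MUSC Biostatistics core until the last 6-month visit is complete and the data are locked, with release to the PI and IRB only where a safety question requires it.

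The cost is a sentence or two of protocol wording and no extra staff. Reporting of serious adverse events and unanticipated device effects is unaffected. The downside is that investigators wait until the end for comparative results.

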Patients with sarcomas who receive preoperative radiation have over twice the incidence of wound complications (35%) when compared to those who receive post-operative radiation (17%)[1]. Postoperative surgical site wound healing problems pose a significant challenge to the orthopaedic oncologist, especially in wounds that have been previously irradiated with neoadjuvant external beam radiation therapy (EBRT). Wound healing after major oncologic resection in the lower extremity is often compromised. In sarcoma patients this is especially true where patients tend to be older than age 50 and most receive preoperative radiation prior to resection to assist in local control. There are many studies demonstrating the relatively high risk of wound complications after lower extremity sarcoma resection. Published data suggest that these preoperatively radiated wounds have a postoperative infection rate of 17%-44% with “traditional” dressings (e.g. dry gauze surgical dressings) [2]. A prospective series from Canada of 190 patients and showed a wound complication risk of 35% in preoperative irradiated wounds [1]. The morbidity associated with wound complications can range from moderate (prolonged dressing changes) to severe (life or limb threatening infection) [3]. The exact cause of the high rate of post-operative wound complications is not well understood.

The choice for timing of radiation is controversial [1]. However, most sarcoma surgeons favor the short term risk of preoperative radiation and its associated wound complications over higher risk of late radiation effects associated with post-operative radiation. These complications are often dose related and difficult to treat and for many patients are permanent. Extremity fibrosis, arthrofibrosis of adjacent joints, chronic edema, and fractures (that are difficult to achieve union) can be debilitating to patients. These late effects of radiation cause many treating surgeons to favor preoperative radiation.

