Analytic Approaches: To assess specific aim one patients will be followed longitudinally for the development of a wound complication and incidence of secondary procedures. Criteria for a wound complication are listed above. The data will be collected prospectively during routine follow up care of the patient and will include presence of absence of wound complication. The proportion of patients with a wound complication will be estimated and the 95% confidence for the true wound complication rate will be calculated with an exact binomial procedure. Although it is not the primary analysis, we will also compare the complication rates across the two groups using a Fisher's exact test (although the study is underpowered for this analysis). We will also use a logistic regression analysis where we adjust for center (using indicator variables) to estimate the overall wound complication rate in each group. For the risk of secondary interventions, the incidence of procedures performed for wound complications will be collected and multiple logistic regression analysis will be used to adjust these procedures in the incidence of wound complications.

To assess specific aim two the total cost of perioperative and post-operative care will be estimated from hospital billing records for patients. The median cost for the NPWT group and control group will be estimated and compared with independent t-test for normally distributed data and the Mann-Whitney test for any nonparametric data. A post hoc analysis of the cost of treatment for each arm will provide comparative effectiveness data for the use of NPWT in preoperatively radiated sarcoma surgical wounds. This is come directly from hospital and clinic charges, dressing and medication costs, and direct societal cost estimates from time missed from work.

Sample size justification: This is a pilot study with the primary objective of estimating complication rates in our patient population using NPWT and traditional dry dressings. We estimate that each of four institutions can enroll a least 40 patients over 36 months for a total of 160 patients. Assuming up to 5 patients in each group will have inevaluable data or follow-up, we plan on a total of 75 evaluable patients in each group. With 75 patients in each group and assuming complication rates of 10% to 30%, we have the following $\frac{1}{2}$ widths for 95% confidence intervals.

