Table 3: Precision of estimates of wound complication rates based on a sample size of 75 for observed complication rates ranging from 11% to 30%.

Observed wound complication rate (N=75)	95% Confidence Interval	Half-width of 95% confidence interval
11%	(4.7% , 20.0%)	7.6%
15%	(7.6%, 24.7%)	8.6%
20%	(11.6%, 30.8%)	9.6%
25%	(16.0%, 36.7%)	10.4%
30%	(20.5%, 42.4%)	10.9%

References:

1. O'Sullivan, B., et al., *Preoperative versus postoperative radiotherapy in soft-tissue sarcoma of the limbs: a randomised trial*. Lancet, 2002. **359**(9325): p. 2235-41.
2. Kunisada, T., et al., *Wound complications following pre-operative radiotherapy for soft tissue sarcoma*. Eur J Surg Oncol, 2002. **28**(1): p. 75-9.
3. Tseng, J.F., et al., *The effect of preoperative radiotherapy and reconstructive surgery on wound complications after resection of extremity soft-tissue sarcomas*. Ann Surg Oncol, 2006. **13**(9): p. 1209-15.
4. Barwick, W.J., et al., *Vascularized tissue transfer for closure of irradiated wounds after soft tissue sarcoma resection*. Ann Surg, 1992. **216**(5): p. 591-5.
5. Peat, B.G., et al., *Wound-healing complications after soft-tissue sarcoma surgery*. Plast Reconstr Surg, 1994. **93**(5): p. 980-7.
6. Davis, A.M., et al., *Function and health status outcomes in a randomized trial comparing preoperative and postoperative radiotherapy in extremity soft tissue sarcoma*. J Clin Oncol, 2002. **20**(22): p. 4472-7.
7. Zhu, F.J., [Thirty-eight cases of abdominal incisional fat necrosis after gynecologic operation treated with moxibustion]. Zhongguo Zhen Jiu, 2012. **32**(8): p. 683-4.
8. Stannard, J., *Complex orthopaedic wounds: prevention and treatment with negative pressure wound therapy*. Orthop Nurs, 2004. **23 Suppl 1**: p. 3-10; quiz inside back cover, back cover.
9. Stannard, J.P., et al., *Negative pressure wound therapy after severe open fractures: a prospective randomized study*. J Orthop Trauma, 2009. **23**(8): p. 552-7.
10. Hansen, E., et al., *Negative pressure wound therapy is associated with resolution of incisional drainage in most wounds after hip arthroplasty*. Clin Orthop Relat Res, 2013. **471**(10): p. 3230-6.
11. Goldstein, J.A., et al., *The use of negative pressure wound therapy for random local flaps at the ankle region*. J Foot Ankle Surg, 2010. **49**(6): p. 513-6.

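### The plan names no NPWT-versus-dry-dressing difference with a confidence interval for wound complications, and its only test of that rate ignores the site blocks

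*Combined protocol and SAP*

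**What the plan says.** Section A states the hypothesis that NPWT "will significantly reduce the incidence and cost of wound complications". Specific Aim 1 is phrased as estimating the complication rate under each dressing, and the sample size justification describes a pilot whose primary objective is that estimation.

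The Research Design section says "Randomization will be done by block randomization per site", and its Randomization paragraph gives the purpose: "Randomization will be predefined at each site using block randomization to ensure that each site is balanced for each arm of the study".

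Under Statistical Considerations, Analytic Approaches, three analyses address the wound complication rate:

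1. The proportion with a complication, with an exact binomial 95% interval.
2. A between-group comparison, declared not primary, by Fisher's "exact test (although the study is underpowered for this analysis").
3. A logistic regression with center indicators, whose stated purpose is "to estimate the overall wound complication rate in each group".

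The sample size paragraph plans 75 evaluable patients per group, "assuming complication rates of 10% to 30" percent. Table 3 is titled "Precision of estimates of wound complication rates based on a sample size of 75" and runs from 11% to 30%. The Background cites a prospective series that "showed a wound complication risk of 35% in preoperative irradiated wounds".

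**The concern.** The hypothesis is about a difference, and randomization is there to identify a difference. Yet for wound complications the only comparative output the plan names is a p-value from a test it already calls underpowered. Subtracting the two estimated rates gives a point difference but no prespecified interval. The center-adjusted model could give both, but its assigned output is the rate in each group. The scale of the contrast, the adjustment and the interval method are therefore open to choice after the data are seen.

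Two smaller points go with this. Fisher's test does not use the site strata within which patients are randomized, and it is conservative at this sample size. Table 3 stops at 30%, below the 35% that the Background gives for preoperatively irradiated wounds.

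What is at stake is how useful the result will be. Anyone planning a larger trial from this pilot needs the difference and its uncertainty.

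**Working it through.** **Inputs.** From the documents: 75 evaluable per arm; rates of 10% to 30% (Sample size justification); 35% in preoperatively irradiated wounds (Background); blocks within site; four institutions (Sample size justification) or six sites (Research Design). Assumed, because the documents do not state them: two-sided alpha 0.05, an NPWT rate of 17.5% (half of 35%) for the main power figures, and the between-site spread.

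**1. The plan's own figures.** Enrollment: 4 × 40 = 160, and (160 − 2 × 5)/2 = 75 per arm. Clopper-Pearson 95% intervals at n = 75 with 8, 11, 15, 19 and 23 events give half-widths of 7.6, 8.6, 9.6, 10.4 and 10.9 points. All five Table 3 half-widths reproduce, so the table describes one arm's rate.

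**2. The missing 35% row.** 26/75 = 34.7%. The exact interval is 24.0% to 46.5%, half-width 11.3 points, against a stated maximum of 10.9.

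**3. Precision of the difference.** Half-width = 1.96 × √[0.35 × 0.65/75 + p(1 − p)/75], where p is the NPWT rate. At p = 0.175 this is 1.96 × √[(0.2275 + 0.1444)/75] = 1.96 × 0.0704 = 13.8 points.

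| NPWT rate | Half-width of difference (points) |
|---|---|
| 10% | 12.8 |
| 17.5% | 13.8 |
| 20% | 14.1 |
| 25% | 14.6 |
| 30% | 15.0 |

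**4. Fisher's conservatism.** Full enumeration of 75 versus 75, control rate 35%:

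| NPWT rate | Fisher power | Pearson chi-square power |
|---|---|---|
| 15% | 77% | 82% |
| 17.5% | 62.6% | 69.0% |
| 20% | 47% | 54% |
| 25% | 21% | 26% |

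At a common rate of 35%, the actual size is 3.3% for Fisher and 5.0% for Pearson. At 17.5% the gain is 69.0 − 62.6 = 6.4 points, and it comes from dropping conservatism, before any stratification.

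**5. Using the site strata.** Simulation with 40,000 trials per setting, four equal sites, arm-level rates held at 35% and 17.5%, and site log-odds SD assumed at 0, 0.5 or 0.8:

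| Test | SD 0 | SD 0.5 | SD 0.8 |
|---|---|---|---|
| Fisher | 62.4% | 62.9% | 62.8% |
| Pearson, unstratified | 68.8% | 69.7% | 69.7% |
| CMH, uncorrected | 69.1% | 71.4% | 73.3% |
| CMH, continuity-corrected | 61.9% | 64.3% | 66.3% |

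Six equal sites give similar results (uncorrected CMH 69.5%, 70.3%, 72.8%). Over Pearson, stratifying adds about 0, 2 and 4 points in these runs. An independent repeat gave about 0, 1 and 3. The size of uncorrected CMH stays at about 5%, including with very unequal sites, where its power is 69% to 72%.

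**6. Does the proposed estimate behave?** In the same settings, the 95% CI for the Mantel-Haenszel risk difference covers 94.6% to 94.9%, with mean half-width 13.0 to 13.8 points. The risk difference standardized from the logistic model (6,000 trials per setting, delta method) covers 94.0% to 94.6%, with half-width 12.7 to 13.6 points.

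**The case against.** The strongest reply is that this is a declared pilot. Its stated objective is estimation by arm, the sample size and Table 3 serve that objective, and the comparison is openly secondary and underpowered. Center is not ignored either: a model that yields center-adjusted rates by group needs a treatment term, so an odds ratio and its interval come from the same fit. Fisher's test keeps its size below 5%, and replacing it partly spends that margin. Unstratified Pearson can reach about 5.6% at a common rate near 44%. The power figures rest on an assumed effect, which matters more than the choice of test, and the benefit of stratifying could be nil. The 35% row moves the largest half-width by only 0.4 points. The documents describe no specific later trial.

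Much of this stands, and it limits the weight of the point. The primary analysis is not wrong, type I error is not inflated, and most of the power gain comes from leaving Fisher, not from using the strata. The 35% row is minor. None of it supplies the missing item. No passage names a between-arm contrast, its scale, its interval or its expected precision. That the planned model could produce one is a reason to name it in advance.

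**Conclusion.** The concern holds, as an inexpensive improvement and not a flaw that invalidates the plan. For wound complications, the hypothesis is comparative but no treatment effect with a confidence interval is prespecified. The unstated precision is about ±12.8 to ±15.0 points, given 75 per arm, a 35% control rate and an NPWT rate of 10-30%. That is wider than any half-width in Table 3.

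The choice of test is secondary. At 35% versus 17.5%, two-sided 0.05, Fisher gives up about 6 points of power through conservatism. Ignoring site costs a further 0 to 4 points or so, depending on an assumed between-site spread. The target rate, alpha, sidedness and site spread are assumptions of this check. The missing contrast and the half-widths for the difference do not depend on them.

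**What to change.** - Keep the exact per-arm intervals as the primary output.
- In Analytic Approaches, prespecify the center-adjusted risk difference, NPWT minus dry dressing, with a 95% CI. Obtain it by standardization from the planned logistic model (treatment plus center indicators) or by the Mantel-Haenszel method. Choose one in advance and state how very small sites will be pooled.
- Replace Fisher's test with a site-stratified CMH test without continuity correction, still labelled non-primary. The corrected version (62-66% power) loses most of the gain.
- In Table 3, add a 35% row (24.0% to 46.5%, half-width 11.3 points) and a line for the difference: about ±14 points at 35% versus 17.5%, and 12.8 to 15.0 across NPWT rates of 10% to 30%.

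The cost is a few sentences, two table lines and a few lines of code. Sample size, data collection and the primary output do not change.
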